15.3.3. Assessment Window for Phase Conclusion

The ‘Phase Conclusion’ records in disposition data will be slotted based on [Table 8](#) (for Maintenance Phase conclusion records) and [Table 9](#) (for Extension Phase conclusion records). However, if the discontinuation date is post-treatment per [Table 16](#), the record will be slotted to the last on-treatment visit within the same phase rather than follow up.

15.3.4. Assessment Window for Health Outcome Data

15.3.4.1. PIN / HAT-QoL / HIVTSQs / HIVTSQc / ACCEPT / Preference

PIN, HAT-QoL, HIVTSQs, HIVTSQc, ACCEPT and Preference questionnaire assessments will be assigned to analysis visits as follows:

1. Baseline will be defined as last available recorded value up to and including the Maintenance treatment start date (expected to be collected at Day 1). Baseline is not applicable for PIN, HIVTSQc and Preference assessments.
2. For post-baseline visits, if the nominal visit identifier as captured in the source dataset corresponds to a scheduled collection per the Time and Events Schedule (see Section 15.2 and [Table 12](#)) and the assessment is collected in the Maintenance Phase (per [Table 14](#)), then the nominal visit identifier will be kept as the analysis visit.
3. For post-baseline visits, if the nominal visit identifier is unscheduled or withdrawal, then the following procedure will be used:
 - a) Assign the assessment to a study phase according to [Table 14](#). Proceed to step b if the assessment is assigned to the Maintenance Phase.
 - b) Identify the ‘last nominal visit’ with the HO assessment performed prior to the unscheduled/withdrawal visit to be slotted.
 - c) The unscheduled/withdrawal visit will be slotted to the planned nominal visit subsequent to the ‘last nominal visit’. If the ‘last nominal visits’ does not exist (e.g. no records originate from a planned nominal visit), then the unscheduled/withdrawal visit will be slot to the first planned nominal visit after Day 1.

Example 1, for HATQoL, the planned nominal visits are Day 1, Week 24, and 48. If a participant has the ‘last nominal visit’ (with HATQoL assessment) at Week 24 prior to withdrawal at Week 36, the withdrawal assessment will be slotted to the subsequent planned nominal visit of Week 48.

Example 2, for HATQoL, if there is unscheduled visit between Week 24 and Week 48. This unscheduled visit will be slotted to Week 48 per the rule. In this case, there are two assessments with analysis visit equal to Week 48 (i.e. the slotted value and the value at

original nominal week 48 visit). The original nominal value will be selected for summary per the rule below for multiple records—see Section 15.3.6.

Table 12 Planned Nominal Visit of Health Outcome Data

Questionnaire	Day 1	Week 8	Week 24	Week 48
PIN		X	X	X
HAT-QoL	X		X	X
HIVTSQs	X		X	X
HIVTSQc				X
ACCEPT	X		X	X
Preference				X
NOTES: Day 1 visits are recorded as “Baseline” visits in the database.				

15.3.4.2. Reasons for Continuation/Switch

Reasons for Continuation/Switch assessments are planned to be taken at nominal Baseline (Day 1) visit only. The assessments taken within ± 2 weeks window from maintenance phase treatment start date will be regarded as evaluable. The assessments taken outside this window will be excluded from the summary.

15.3.5. Assessment Window for PK Concentration Data

For PK concentration data at the withdrawal/unscheduled/LTFU Month 1 visits during maintenance phase (after assignment to study phase per Table 14), the visit will be slotting to the analysis visit per the following steps:

- Identify the ‘last nominal visit’ with the PK pre-dose assessment performed prior to the visit to be slotted during the same study phase
- Identify the nominal visit corresponding to the next planned pre-dose PK assessment visit (excluding visits with storage PK collection), that is subsequent to the ‘last nominal visit’ with PK pre-dose assessment during the same study phase.
- If the nominal visit corresponding to next planned pre-dose PK assessment visit is prior to/at Week 48 visit, the PK assessment at the unscheduled/withdrawal/LTFU Month1 visit will be slotted to this nominal visit corresponding to next planned pre-dose PK assessment visit.
- Otherwise, the PK assessment at the unscheduled/withdrawal/LTFU Month1 visit will be slotted to the earliest nominal visit from the following:
 - Nominal visit corresponding to the next planned pre-dose PK assessment visit
 - The nominal visit of the next planned injection occurring on or after the date of the PK assessment during the same study phase

During maintenance phase, the planned nominal visits for PK Pre-dose are Week 4B, 8, 16, 24, 32, 40, 48, 96 for Q4W arm; and are Day 1, Week 4B, 8, 16, 24, 32, 40, 48, 96 for

Q8W arm while Day 1 is required only for those transitioning from ATLAS on Q4W injections and Week 4B is required only for participants transitioning from oral SOC and requiring oral CAB+RPV lead-in. In addition, the participants on Q8W arm have planned nominal visits at Week 9 and 41 for 1-week post-dose.

For participants requiring oral CAB+RPV lead-in, the planned injection visits are Week 4B, Week 8, continuing every 4 weeks for Q4W arm and continuing every 8 weeks for Q8W arm. For participants not requiring oral CAB+RPV lead-in, the planned injection visits are every 4 weeks starting from Day 1 for Q4W arm and every 8 weeks starting from Day 1 for Q8W arm.

Example 1: If a participant on Q8W arm has the ‘last nominal visit’ (with PK pre-dose assessment) at Week 24 and then withdraws around Week 28, with the last injection at Week 24 and a Maintenance Phase PK assessment labelled at ‘LTFU Month 1’, This PK assessment labelled as ‘LTFU Month 1’ will be slotted to the subsequent planned nominal visit of Week 32.

Example 2: If a participant on Q4W arm has the ‘last nominal visit’ (with PK pre-dose assessment) at Week 48 and then have an unscheduled Maintenance Phase PK assessment around Week 74. This assessment will be slotted to the next planned injection visit, Week 76.

There will be no slotting for planned nominal visits (i.e. analysis visit =visit).

15.3.6. Multiple Assessments within an Assessment Window

If after window assignment there are multiple valid assessments of a parameter within the same window, then the following hierarchy will be used to determine the value to be used for summary statistics of observed values:

For data other than health outcome/PK concentration:

1. the assessment closest to the window target Study Day;
2. if there are multiple assessments equidistant from the target Study Day, then the mean of these values will be used. For HIV-1 RNA, the geometric mean of the number of copies will be used as opposed to the arithmetic mean.

For Health outcome and PK concentration data, the following hierarchy will be used to determine the value to be used for summary statistics of observed values:

1. If there are multiple on-treatment assessments assigned to the same analysis visit, the assessment from the planned nominal visit will be used for summary statistics.
2. If there are multiple on-treatment assessments assigned to the same analysis visit and none originates from a planned nominal visit (e.g. two unscheduled/withdrawal nominal visits), then
 - a. the assessment closest to the window target Study Day will be used;
 - b. if there are multiple assessments equidistant from the target Study Day, then the earliest assessment will be used.

Assessments not chosen for use in summary statistics by this algorithm will still appear in the associated listings. Also, all applicable valid assessments, irrespective of proximity to the target study day, will be used when categorizing values across visits, such as 'maximum grade' or 'at any time', and for any algorithm that has specific rules for which observation to use (e.g. snapshot algorithm, LOCF or CVF identification).

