15.2.2. Protocol Defined Schedule of Events for Q8W Arm

Procedure	Screening Visit ^a	Maintenance Phase																			Extension Phase	Withdrawal Assessments ^y	Long-Term Follow-up ^z					
		Day 1	Week																									
			Week 4A (Oral lead-in ONLY) ^b	Week 4B (Oral lead-in ONLY) ^b	8	9	16	24	32	40	41	48	56	64	72	80	88	96	100	Q8W After Week 96								
Written informed consent	X																											
Eligibility Verification (Inclusion/ Exclusion Criteria)	X		X ^c																X ^c									
Randomization		X																										
Demography	X																											
Medical History ^d	X																											
Cardiovascular risk assessment ^d	X	X																										
Medication History/ Prior ART history	X																											
Syphilis serology + reflex Rapid Plasma Reagin (RPR)	X	X																										

Procedure	Screening Visit ^a		Maintenance Phase																	Extension Phase	Withdrawal Assessments ^y	Long-Term Follow-up ^z			
	Day 1	Week																							
		Week 4A (Oral lead-in ONLY) ^b	Week 4B (Oral lead-in ONLY) ^b	8	9	16	24	32	40	41	48	56	64	72	80	88	96	100	Q8W After Week 96						
Symptom Directed Physical Exam and Medical Assessment ^e	X	X	X	X	X	X	X	X	X	X	X	X	X	X	X	X	X	X	X	X	X	X	X	X	X
Weight, Height and BMI ^f		X									X							X						X	
Vital Signs (BP, HR, Temperature) ^g	X	X									X							X						X	
12-lead ECG ^h (triplicate at Day 1 pre-dose)	X	X									X							X						X	
CDC HIV-1 stage	X	X																							
HIV Associated Conditions		X	X	X	X	X	X	X	X	X	X	X	X	X	X	X	X	X	X	X	X	X	X	X	X
AEs, SAEs, Concomitant Medications	X _i	X	X	X	X	X	X	X	X	X	X	X	X	X	X	X	X	X	X	X	X	X	X	X	X
ISR Assessment for IM injection		X		X	X	X	X	X	X	X	X	X	X	X	X	X	X	X	X	X	X	X	X	X	X

Procedure	Screening Visit ^a		Maintenance Phase																	Extension Phase	Withdrawal Assessments ^y	Long-Term Follow-up ^z
	Day 1	Week																	Q8W After Week 96			
		Week 4A (Oral lead-in ONLY) ^b	Week 4B (Oral lead-in ONLY) ^b	8	9	16	24	32	40	41	48	56	64	72	80	88	96	100				
Columbia Suicide Severity Rating Scale (eC-SSRS) ^j	X	X		X	X		X	X	X	X		X	X	X	X	X	X	X			X	
Clinical chemistry and Hematology	X	X	X	X	X		X	X	X	X		X	X	X	X	X	X	X	X	X	X	X
Pregnancy Testing ^k	S	U	S	U	S		S	S	S	S		S	S	S	S	S	S	S	S	S	S	S
HIV-1 RNA and sample for storage (S) ^l	X	X		X	X		X	X	X	X		X	X	X	X	X	X	X	S	X	X	X
CD4+ cell count	X	X		X	X		X	X	X	X		X	X	X	X	X	X	X	X	X	X	X
CD8+ cell count		X						X				X						X			X	
Urinalysis ^m		X	X					X				X						X			X	

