- a. Participants may be rescreened once and will be assigned a new participant number. Participants transitioning from the 201585 (ATLAS) study must reach ATLAS Week 48 (at minimum) prior to initiating Screening procedures for ATLAS-2M and must reach ATLAS Week 52 (at minimum) prior to randomization in ATLAS-2M.
- b. Visits Weeks 4A and 4B are part of the CAB + RPV Oral Lead-in period and are required only for participants transitioning from current SOC to CAB LA + RPV LA.
- c. Confirmation of eligibility to continue the Maintenance Phase, and eligibility to enter the Extension Phase.
- d. Collect full routine medical history plus (report at Baseline visit): HIV risk factors (may be collected at a later study visit), cardiovascular risk factors (assessments include smoking status and history, family history of cardiac events), recent [≤ 6 months] illicit drug use, intravenous drug use, gastrointestinal disease, metabolic, psychiatric, renal, bone, and neurologic disorders.
- e. Physical exams should be conducted as part of normal routine clinical care. Medical assessments include any decisions the study staff must make for participants management and/or care of participant.
- f. Height collected at Baseline Day 1 only.
- g. Measure vital signs after about 5 minutes of rest in a semi-supine position.
- h. A 12-lead ECG will be performed after resting in a semi-supine position for at least 5 minutes. ECGs will be performed pre-dose. For participants transitioning from ATLAS, the pre-dose Week 48 ECG can also serve as the ATLAS-2M Screening ECG. ECG pre-dose will be performed in triplicate at Day 1. A 2-hour post-dose ECG will also be performed at Days 1 and Week 48 for participants receiving CAB LA + RPV LA with an allowable window of ± 30 minutes.
- i. Only SAEs related to study participation or to a concomitantly administered ViiV/GSK product will be collected between obtaining informed consent and administration of study drug at Day 1.
- j. On Day 1, the eC-SSRS is to be administered prior to randomization. The eC-SSRS will preferably be completed at the beginning of the visit following administration of other PROs required prior to injections. The eC-SSRS is not required during the Withdrawal visit if withdrawal occurs during the Extension Phase.

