15.3. Appendix 3: Assessment Windows

15.3.1. Definitions of Assessment Windows for Analyses

Laboratory data, vital signs, ECGs, health outcomes assessments, and genotypic/phenotypic data will be assigned to assessment windows according to actual dates rather than the nominal visit labels as recorded on the eCRF or in the laboratory database.

In most cases the window around an assessment will include all dates from the midpoints between the target day and that of the previous and the proceeding visits. In general, the nominal target study day for week w is $(7*w)+1$.

For parameters which are not scheduled to be assessed at particular visits, the all-inclusive assessment windows will still be used; however, data summaries will only report scheduled visits. Assessments at unscheduled visits will be included for ‘any time On-treatment’ time points and in data listings, as well any algorithms that make use of additional data (e.g., Snapshot).

Prior to visit slotting, assessments are first assigned to a study phase (screening, maintenance, extension, or long-term follow-up) based on the Tables in Section 15.4.1 and treatment state based on Section 15.4.2.

Maintenance phase assessments other than health outcome and PK are assigned based on the Study Day as shown in Table 8 and Table 10. Table 8 also includes visiting slotting for screening assessments. The analysis visits from Week 4 to Week 100 should be only applied to the assessments that are already assigned to Maintenance phase (on-treatment). Extension phase assessments other than health outcome and PK are assigned based on the Study Day as shown in Table 9. The analysis visits from Week 104 (except for Follow-up) in the Extension phase should be only applied to the assessments that are already assigned to Extension phase (on-treatment).

Long-term Follow-up phase assessments are assigned based on the LTFU study day as shown in

Table 11. The analysis visits in LTFU should be only applied to the assessments that are already assigned to LTFU phase regardless of treatment state. See Section 15.6.1, for derivation of Study Day and LTFU Study Day.

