15.3.2. Definitions of Assessment Windows for Analyses other than Health Outcome and PK

Table 8 Assessment Windows for Screening and Maintenance Phase Data

All Parameters except for where noted ^[c]	Target Study Day	Analysis Window	Analysis Timepoint
	The study day of first record	Study Day \leq 1	Screening
	1	Last available recorded value up to and including the Maintenance treatment start date, excluding 2-hour post-dose ECG taken on the Maintenance treatment start date	Baseline
Urinalysis ^[a]	29	$2 \leq$ Study Day \leq 70	Week 4
		$2 \leq$ Study Day \leq 42, including 2-hour post-dose ECG taken on Maintenance treatment start date	
	57	$43 \leq$ Study Day \leq 84	Week 8
	113	$85 \leq$ Study Day \leq 140	Week 16
Urinalysis ^[a] , CD8, CD4/CD8 ratio	169	$141 \leq$ Study Day \leq 210	Week 24
		$141 \leq$ Study Day \leq 196	
	225	$197 \leq$ Study Day \leq 252	Week 32
	281	$253 \leq$ Study Day \leq 308	Week 40
Urinalysis ^[a] , fasting glucose, lipids ^[b] , CD8, CD4/CD8 ratio, weight, vital signs, ECG	337	$309 \leq$ Study Day \leq 378	Week 48
		$309 \leq$ Study Day \leq 364	
	393	$365 \leq$ Study Day \leq 420	Week 56
	449	$421 \leq$ Study Day \leq 476	Week 64
	505	$477 \leq$ Study Day \leq 532	Week 72
	561	$533 \leq$ Study Day \leq 588	Week 80
	617	$589 \leq$ Study Day \leq 644	Week 88
Urinalysis ^[a] , fasting glucose, lipids ^[b] , CD8, CD4/CD8 ratio, weight, vital signs, ECG	673	$645 \leq$ Study Day \leq 714	Week 96
		$645 \leq$ Study Day \leq 686	
	701	$687 \leq$ Study Day \leq (Study Day of Nominal Week 100 visit)	Week 100
If a participant permanently discontinued study treatment:			
		For Participants on Q8W Arm: Date > max (Date of Last Oral Dose of CAB+RPV + 1, Date of	Follow-up

All Parameters except for where noted ^[c]	Target Study Day	Analysis Window	Analysis Timepoint
		Last Injection + 63)	
		For Participants on Q4W Arm: Date > max (Date of Last Oral Dose of CAB+RPV + 1, Date of Last Injection + 35)	

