Maintenance	For participants continuing into Extension Phase: Maintenance Treatment Start Date < Date \leq Date of Nominal Week 100 Visit Note: 2-hour post-dose ECG taken on the Maintenance Treatment Start Date will be included. For participants not continuing into Extension Phase^[a]: Maintenance Treatment Start Date < Date \leq LTFU ART Start Date Note: 2-hour post-dose ECG taken on the Maintenance Treatment Start Date will be included.
Extension	Participants continuing into Extension Phase^[a]: Date of Nominal Week 100 Visit < Date \leq LTFU ART Start Date

- Date = start or assessment date
- [a] If participants have missing LTFU ART start date (i.e. the participants have not started ART in LTFU yet), only the lower bound of the window will be considered in the derivation.

Table 15 Assignment to Long-term Follow-up Phase

Study Phase	Definition
Long-term Follow-up	Date > max (Last IM Injection Date, Last Oral Bridging End Date)

- Date = Assessment/Start Date
- For AEs leading to withdrawal and started on the same date as LTFU ART Start Date, maintenance phase or extension phase depending on participant's continuation status to extension phase, instead of long-term follow-up phase, will be assigned. Refer to [Table 13](#) for details.

Only participants who received at least one CAB and/or RPV injection will enter the long-term follow-up. Note that the long-term follow-up phase and maintenance/extension phases are not necessarily mutually exclusive and are to be defined with separate phase variables in the datasets. For example, an Q4W IM participant who has Week 44 injection and withdrawal at Week 48 without receiving Week 48 injection, the “Week 48 withdrawal visit” belongs to both the maintenance phase and long-term follow-up phase.

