
 • Unscheduled visits will be assigned to a study visit using the all-inclusive windows defined in Section 15.3. • However, data summaries will only report visits that are planned assessment time points for each parameter (according to the Time and Events table). • Assessments at unscheduled visits will be included for 'any time On-treatment' time points and in data listings, as well any algorithms that make use of additional data (e.g., Snapshot). 	
Descriptive Summary Statistics	
Continuous Data	Refer to IDSL Statistical Principle 6.06.1
Categorical Data	N, n, frequency, %
Graphical Displays	

 • Refer to IDSL Statistical Principals 7.01 to 7.13. 	

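### By-visit ECG summaries have no separate 2-hour post-dose value: Week 48 pre-dose and post-dose ECGs are averaged, and the Day 1 post-dose ECG is slotted to Week 4

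*SAP*

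**What the plan says.** **ECG schedule.** Footnote h in 15.2 has ECGs taken before dosing and adds: "A 2-hour post-dose ECG will also be performed at Days 1 and Week 48 for participants receiving CAB LA + RPV LA". The wording is the same for both arms. The Q8W schedule (15.2.2) plans ECGs at Screening, Day 1 ("triplicate at Day 1 pre-dose"), Week 48, Week 96 and Withdrawal. It has none at Week 4.

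**Windows.** Section 15.3.1 assigns ECGs by actual date, not nominal visit, and states that "the nominal target study day for week w is" 7w + 1. Table 8 (15.3.2) gives ECG a single Week 48 window, Study Days 309 to 378 with target Day 337. It does not split pre-dose from post-dose.

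**Day 1 post-dose ECG.** Table 8 excludes it from baseline and puts it in the Week 4 window (Days 2 to 42, "including 2-hour post-dose ECG taken on Maintenance treatment start date"). Table 14 (15.4.1) assigns it to the Maintenance Phase: "2-hour post-dose ECG taken on the Maintenance Treatment Start Date will be included".

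**Several values in one window.** For data other than health outcomes and PK, 15.3.6 takes the value closest to the target day and then, for ties, "if there are multiple assessments equidistant from the target Study Day, then the mean of these values will be used". The same section uses every valid assessment when values are categorised across visits, and keeps unselected values in listings.

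**What is reported.** Section 15.3.1: "data summaries will only report scheduled visits". Section 15.5.2, under unscheduled visits: "data summaries will only report visits that are planned assessment time points for each parameter". Both sections keep unscheduled values for any-time on-treatment rows and for listings.

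**The concern.** The SAP treats the post-dose ECG as a different kind of measurement, because it takes care to keep it out of baseline. After baseline it makes no such distinction. The window and tie rules merge the Week 48 post-dose ECG with the pre-dose ECG of the same day. They also move the Day 1 post-dose ECG to a visit four weeks later at which no ECG is planned. PK data, by contrast, have separate pre-dose and 1-week post-dose timepoints (15.3.5, 15.6.5).

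At stake is whether the by-visit change-from-baseline summary (Table 3.60 in the Week 48 package) can show a mean QTc shift two hours after injection, or compare that shift between arms. QTc prolongation at supratherapeutic doses is listed in 8.2, Table 4, as an event of special interest for RPV, so a reader of the report is likely to look for it there.

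**Working it through.** The SAP gives no figure to reproduce. The check traces the written rules and applies the averaging formula.

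**Week 48**

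1. Target day (15.3.1): 7 × 48 + 1 = 337, inside the ECG window 309 to 378 (Table 8).
2. The pre-dose ECG and the 2-hour post-dose ECG share one date d, so both lie |d − 337| from target. Day 330 gives 7 and 7; Day 337 gives 0 and 0; Day 345 gives 8 and 8. They tie on every date, so the mean rule always applies when both are present.
3. Triplicates are specified only for Day 1 pre-dose, so Week 48 has one pre-dose and one post-dose ECG. Let a be the pre-dose change from baseline and D the post-dose increment over pre-dose. The by-visit value is (a + a + D)/2 = a + D/2.
4. With a = 0 and illustrative values of D (assumptions, not from the SAP):

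| D (msec) | Week 48 by-visit value (msec) |
|---|---|
| 5 | 2.5 |
| 10 | 5 |
| 20 | 10 |
| 60 | 30 |

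5. For the averaged change to reach 60 msec, the post-dose change must be 120 − a: 120 msec if a = 0, 110 if a = 10, 100 if a = 20. This applies to a by-visit row only.
6. Both arms have a planned Week 48 injection, so a between-arm difference in post-dose increment is halved as well.

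**Day 1**

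1. The Week 4 target day is 7 × 4 + 1 = 29. The ECG is taken on Study Day 1, which is 29 − 1 = 28 days earlier.
2. Week 4 is not in the ECG schedule shown. If 15.3.1 and 15.5.2 are applied, the by-visit table does not print the value. If the Table 8 assignment is taken as enough to print it, it appears as a Week 4 result.
3. This concerns only participants who receive injections on Day 1, that is, those transitioning from Q4W injections in ATLAS. Participants from oral standard of care start with the oral lead-in.

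**Where individual values survive**

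- Any across-visit rows in the QTc category tables (3.61 and 3.62) use all valid assessments under 15.3.6.
- Listing 23 shows ECG values for participants with a value of potential clinical importance, with the change from baseline for each QTc assessment.

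**The case against.** The strongest reply is that nothing is lost for safety. Across-visit categories and listings keep each reading, and only Table 3.60 is titled as by visit; 3.61 and 3.62 are by category. This stands. A reader might infer that no table can reflect a post-dose QTc effect, or that a post-dose reading above 500 msec, or a rise of 60 msec, would disappear into an average. The documents do not support either inference. But pooled outlier rows cannot show a mean shift at two hours or set pre-dose beside post-dose by arm.

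Second, the table shells are not in the document and may already carry separate planned-time rows. That cannot be excluded. Such rows would, however, conflict with the written rules in Table 8 and 15.3.6, and the exception would still have to be written.

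Third, 15.5.2 says that summaries use actual time relative to dosing unless otherwise stated. This is a general convention. It creates no ECG timepoint and does not displace the specific rule in 15.3.6.

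Fourth, the Day 1 slotting is deliberate and protects baseline, and footnote h does plan that ECG, so its omission from tables is an inference. This is fair, and it is why the result is stated as either omitted or mislabelled. Protecting baseline does not require a Week 4 label.

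Finally, the event-of-special-interest tables are built from MedDRA terms (15.11) and are unaffected, and the SAP does not state why the post-dose ECGs are collected. Both points are correct and limit how much weight Table 4 can carry.

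**Conclusion.** The point holds for by-visit summaries. Under 15.3.1, Table 8 and 15.3.6 as written, Table 3.60, and any by-visit rows in 3.61 and 3.62, contain no separate 2-hour post-dose value. The Week 48 value includes half of any post-dose increment. The Day 1 post-dose value is dropped or carries a label 28 days out. The cause is a stated rule, not missing detail.

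The point does not extend to detection of outliers: individual QTc values remain available to across-visit categories and listings. This is a defect in a descriptive safety summary, worth correcting before the tables are programmed.

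The conclusion assumes one pre-dose and one post-dose ECG at Week 48, as the schedule implies, and shells that follow the SAP text. The ECG row of the Q4W schedule is not visible in the text available. The same footnote applies there, so the Week 48 reasoning carries over.

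**What to change.** - In 15.3.6 and Table 8, define three separate ECG analysis timepoints: Day 1 2-hour post-dose, Week 48 pre-dose, and Week 48 2-hour post-dose.
- Limit the mean rule for ECG to replicates at the same planned time, so that pre-dose and post-dose readings are never combined.
- Remove the Day 1 post-dose ECG from the Week 4 window. Keep its exclusion from baseline and its Maintenance Phase assignment in Table 14.
- Show these timepoints by arm as rows in Table 3.60 and in any by-visit rows of 3.61 and 3.62. Note that the Day 1 post-dose row covers only participants injected on Day 1.

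The cost is a few lines of SAP text and two extra table rows. The ECGs are already scheduled, so no new data are needed.
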